**Will follow-up procedures be performed specifically for research purposes?**

**Follow-up procedures may include phone calls, interviews, biomedical tests or other monitoring procedures.**

\* Yes

Detailed procedures listed in the textbox below:

Following the epidural placement the patient will be asked to rate their satisfaction and anxiety levels during the procedure. The patient will again be followed up with in their hospital room within 24 hours of their delivery to assess for any complications related to their epidural placement and to administer the modified WOMBLSQ questionnaire. Following that visit no further participation from the patient is anticipated. Should they present afterwards with an epidural-related complication, that information will be collected and included in the study.

Use of Ultrasound Guidance to Assist with Labor Epidural Placement in Patients with a BMI ≥ 40

NCT02984267

Date: 10/1/2016

Statistical analysis plan

The primary outcome is total time (minutes) to successful epidural catheter placement, defined as the sum of the ultrasound or palpation time, plus the epidural catheter placement time. The present study focused on the morbidly obese population ($BMI \geq 40$), of which we are unaware of any available data to guide a calculation for the primary outcome. Based on pilot data means and variances, total sample size will be calculated with 80% power to detect a six-minute difference in time-to-placement between groups with an alpha of 0.05 (two-tailed).

Distribution normality of continuous data will be examined using box plots and histograms. Non-normally distributed data will be compared using the Kruskal-Wallis H test, and continuous data compared with the Mann-Whitney U test. Normally distributed continuous variables will be compared using the independent sample Student t-test. The Fisher Exact test will be used for categorical variables. A P-value of ≤ 0.05 will be considered statistically significant.

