**Study Interventions and Measures:**

The major intervention in this study is the use of ultrasound (US) guidance to assess for correct spinal location prior to epidural placement. This differs from the current standard of care which is to use palpation only to assess for correct spinal location. The outcome measures that will be assessed and evaluated include:

- Total time required for epidural placement\*
- Epidural procedure time\*\*
- Number of epidural attempts needed
- Success rate in the first attempt
- Complication rate including incidence of PDPH and paresthesias
- Incidence of failed epidurals needing to be replaced
- Verbalized patient anxiety and satisfaction levels based on a 1-10 scale
- Modified Woman's Views of Birth Labour Satisfaction Questionnaire (WOMBLSQ) scores

\*Procedure time plus the time needed to locate the puncture site using either palpation or ultrasound guidance, begins when hands or ultrasound probe are applied to the patient

\*\*Time from insertion of the epidural needle to removal of the epidural needle

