**Background: Briefly describe previous findings or observations that provide the background leading to this proposal.**

Placement of labor epidurals is a very common daily practice in obstetrical anesthesia. Currently, these epidurals are placed based upon palpation of landmarks to determine midline and the correct spinal level for placement. Palpation of these landmarks can be difficult, however, particularly in morbidly obese patients who have significant amounts of soft tissue overlying these landmarks which can contribute to an increased number of attempts needed for placement, increased time required to complete the procedure, increased likelihood for complications, and decreased patient satisfaction. In recent years, ultrasound guidance has been increasing in popularity as a way to help visualize the spine and offset these challenges.

Ultrasound guidance is already used in multiple patient populations to assist with many different procedures including neuraxial and peripheral nerve blocks. With regards to peripheral nerve blocks, it is now considered standard of care to use ultrasound guidance to provide visualization when performing nearly any procedure including interscalene blocks, supraclavicular blocks, infraclavicular blocks, axillary blocks, femoral nerve blocks, sciatic nerve blocks, adductor canal blocks, quadratus lumborum blocks, transversus abdominus plane blocks, and others. It is also standard in anesthesiology to use ultrasound guidance to assist with central line placement such as internal jugular or femoral vein central lines. Multiple centers have also begun using it for neuraxial placement such as with epidurals, spinals, or combined spinal epidurals (CSEs). Several researchers such as Carvalho, Vallejo, Chin, Balki, Ansari, and others have explored the use of ultrasound guidance in obstetric patients and found it useful in several ways such as estimating the distance to and more easily locating the epidural space. We hope to continue to expand the current research in this area.

There have been no attempts to date at West Penn Hospital to begin enrolling patients for this study. This was due to the PI (myself) no longer being available at that facility to conduct the research. The PI at that location has since been changed to [name] and they intend to begin data collection within the next month.

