their labor and delivery room appropriately for their epidural and then use either the ultrasound machine (experimental group) or palpation (control group) to mark with a marking pen the desired location for epidural placement. [name] and [name] will be the only providers to mark the patients. Every attempt will be made for them to be available for study patients, but if they cannot be (they are caring for another patient or are no longer in the hospital at the time the epidural is requested) then the patient may have to be dropped from the study. Once the patient has been marked, a second anesthesia provider who will be performing the epidural will come into the room. This second provider will be blinded to whether the marks on the patient were made based upon ultrasound guidance or palpation (the patient will not be blinded). This second provider who will perform the epidural can be any type of experienced provider (attending, fellow, resident, or CRNA) who has already completed at least 40 epidurals in the past. They will then perform the epidural in the standard fashion, using the previously marked site as their initial entry point. If entering at the already marked site does not result in success, the provider performing the procedure may reassess and redirect at their discretion. During epidural placement, the primary investigator ([name] or [name]) will be responsible for timing the procedure and recording the number of attempts required to succeed. Epidurals are typically placed successfully within 5-10 minutes depending on patient anatomy and provider experience.

Following the epidural placement and achievement of pain relief, the patient will be asked to rate their satisfaction and anxiety levels during the procedure. No extra interventions or monitoring specific to this study (i.e. outside of what is already normally performed) will be required.

Patients will be followed up on in their hospital room within 24 hours of their delivery to assess for any complications related to their epidural placement and to administer the modified WOMBLSQ questionnaire. If a complication is detected, treatment will be given as clinically warranted. Following that visit no further participation from the patient will be necessary. This study is projected to take about 6 months to complete.

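### Is a six-minute planning difference out of reach when the protocol says epidurals typically take 5-10 minutes?

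*SAP*

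**What the plan says.** The SAP's first paragraph makes total time to successful catheter placement the primary outcome, "defined as the sum of the ultrasound or palpation time, plus the epidural catheter placement time". The protocol's footnote under Study Interventions and Measures agrees: "Procedure time plus the time needed to locate the puncture site using either palpation or ultrasound guidance".

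For the sample size, the same SAP paragraph says that the authors know of no data in the morbidly obese to guide the calculation. The size therefore rests on a pilot: "Based on pilot data means and variances", "total sample size will be calculated with 80% power to detect a six-minute difference in time-to-placement between groups", at a two-sided alpha of 0.05. It gives no pilot mean, pilot SD or resulting number of patients, and no reason for choosing six minutes.

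The one duration in the documents is in the protocol's description of research activities, after the account of how the site is marked and how the second provider proceeds: "Epidurals are typically placed successfully within 5-10 minutes depending on patient anatomy and provider experience". The Background section says that difficult landmarks in morbidly obese patients can lead to more attempts and to "increased time required to complete the procedure", without a figure.

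**The concern.** Set side by side, the two numbers clash. If placement takes 5-10 minutes, a six-minute saving removes most or all of it. Scanning time also counts in the primary outcome, so any minute that ultrasound takes beyond palpation must be recovered in needle time before a net saving appears.

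If six minutes really were out of reach, the stated power would apply to an effect that cannot occur, and the trial would be underpowered for any saving that can. A non-significant result might then be read as showing that ultrasound saves no time. The SAP plans tests and a P-value threshold and mentions no confidence interval that would show which savings had been ruled out.

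A smaller worry concerns the pilot. Once the difference is fixed at six minutes, only the pilot variance enters the formula, and an SD estimated from few patients delivers somewhat less than 80% power on average.

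**Working it through.** **Inputs from the documents.** Difference 6 minutes of total time, power 80%, two-sided alpha 0.05 (SAP, first paragraph); placement time 5-10 minutes (Protocol, description of research activities). Equal allocation is assumed. There is no stated sample size to reproduce.

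**1. The ratio.** 6/10 = 60% and 6/5 = 120%. With an assumed 2 extra minutes of scanning, needle time must fall by 6 + 2 = 8 minutes: 8/10 = 80% and 8/5 = 160%. The arithmetic is right.

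**2. Whether the two figures measure the same thing.**

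| | Six minutes | 5-10 minutes |
|---|---|---|
| Quantity | Locating plus placement | Placement; locating time not mentioned |
| Population | BMI ≥ 40 | Epidurals in general, varying with anatomy and experience |
| Kind of figure | Difference between group means | Typical range |
| Role | Planning input | Description of the procedure |

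They differ on every row. Placement and palpation times for the control arm have to be assumed:

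| Placement + palpation (min, assumed) | Total | 6/total | 6/placement, no extra scanning | (6 + 2)/placement, 2 min extra scanning |
|---|---|---|---|---|
| 5 + 1 | 6 | 100% | 120% | 160% |
| 10 + 2 | 12 | 50% | 60% | 80% |
| 15 + 2 | 17 | 35% | 40% | 53% |
| 20 + 2 | 22 | 27% | 30% | 40% |

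The target is impossible in the first row, hard in the second and feasible in the last two. The documents do not say which row describes these patients. They say only that times are longer in morbid obesity.

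**3. Power at smaller differences.** For a trial sized at 80% for six minutes, power at a true difference d is Φ(2.8016·d/6 − 1.96) plus a negligible opposite tail, where 2.8016 = 1.960 + 0.842.

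- d = 4: Φ(1.868 − 1.96), about 46%
- d = 3: Φ(1.401 − 1.96), about 29%
- d = 2: Φ(0.934 − 1.96), about 15%

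Only d/6 enters. A trial sized at 80% for any target D has the same 46%, 29% and 15% at two-thirds, one-half and one-third of D. The figures therefore say nothing about whether six is the wrong choice. Powering for three minutes would take (6/3)² = 4 times the patients, and for two minutes (6/2)² = 9 times.

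**4. Whether the trial must be small.** Patients per arm = 2·(SD·2.8016/6)². At assumed SDs of 4, 6, 8, 10 and 12 minutes this gives 7, 16, 28, 44 and 63, a nine-fold range. Without the pilot SD, one cannot say that the trial is small. These are normal approximations: with a t-test, 7 per arm at SD 4 has about 73% power at six minutes, and 63 per arm at SD 12 has just under 80%.

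**5. The pilot SD used as if known.** With assumed pilots of 5, 10 and 20 per arm, simulated mean true power is about 73-74%, 77% and 78-79%. The loss is a few points from 10 per arm upward. Using only the pilot SD does not remove it, because the SD is where the uncertainty lies.

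**The case for a change.** The strongest reply is that dividing by total time does not remove the constraint. Unless scanning is quicker than palpating, the whole saving must come out of needle time, so needle time is the denominator that decides feasibility. The only needle-time figure given is 5-10 minutes, and the 15 and 20 minute cases above are assumptions found nowhere in the documents. Even at 10 minutes, a six-minute net saving requires at least a 60% cut.

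The point about the denominator stands, and so does the observation that six minutes is large against the one figure available and comes without a rationale. What does not follow is that the documents rule it out. The figure is a general one, and the protocol expects times above it in this population. A typical range also understates a mean that includes difficult placements: the outcome runs to success, the provider may reassess and redirect when the marked site fails, and these are the cases ultrasound is meant to help.

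The remaining requests add little:

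- A smaller target means several times the patients, or exchanges one debatable effect size for another.
- Sizing from the pilot SD alone gives the same number once the difference is fixed. The mention of pilot means may only record how six minutes was chosen.
- Excluding pilot patients from the analysis answers a problem the documents do not show, since nothing says they will be included.
- Reporting the difference in minutes with a 95% confidence interval is good practice that analysts can supply without a change to the planned test.

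**Conclusion.** The concern does not call for a change. The 60% to 120% is correct arithmetic on two quantities that are not alike, and it cannot show that six minutes is unattainable. Under assumed control totals of 12 to 22 minutes the target is a 50% to 27% reduction in total time. It would be impossible only if control times in BMI ≥ 40 sat near the bottom of the general range, which runs against the protocol's own Background. The lower power at 4, 3 and 2 minutes (46%, 29%, 15%) is what any trial sized at 80% for six minutes would have, and the 80% is a target for a size still to be calculated, not a claim about a stated one.

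What remains is a gap in justification. A reader would be helped by the pilot mean and SD of total time, the resulting number of patients, the power at smaller differences, and the estimated difference with its interval. These are reporting details and leave the planned comparison sound. The conclusion rests on reading the 5-10 minutes as a general description of placement; a pilot control mean of total time near six minutes would reopen the question.

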This study is to be a prospective, randomized, controlled trial of morbidly obese parturients presenting to either West Penn Hospital or Magee Women's Hospital for delivery and desiring epidural anesthesia. Patients will be screened for participation in the study during the standard pre-anesthesia assessment that is already conducted by anesthesia staff on all patients presenting to Labor and Delivery. Screening will include an evaluation of the patient's medical history and BMI. The study will then be explained to patients who satisfy the inclusion and exclusion criteria and informed consent obtained should they choose to participate. A waiting period of 5-30 minutes will elapse between introduction of the study to the participant's consent to participate. At the time the patient is ready to receive their epidural, an opaque, sealed, numeric envelope labeled only with a study number will be opened containing the data collection sheet and randomly assigned group for that participant. These envelopes will be prepared prior to beginning the study by a healthcare provider not involved in the study. An online randomizer (Randomization.org) will be used to generate a random order for assignment to either the ultrasound guidance group (experimental group) or the palpation only group (control group) which will be revealed to the experimenters only upon opening the envelope at the time of epidural request. These envelopes will be distributed in equal numbers to each facility participating in the study at the onset of the study.

Once the patient has progressed in their labor to the point where they request placement of labor epidural analgesia, the primary investigator for that site ([name] at Magee, and [name] and West Penn) will be the one to open the envelope revealing which group the patient has been assigned to. This will occur during the same hospitalization as the screening visit and in many cases within just a matter of minutes to hours after the initial screening and consent process. This same person will then position the patient in

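### Total time is compared only with unadjusted tests; prespecified adjustment for BMI and site is a cheap option whose gain is unknown and which suits only a total N of about 30 or more

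*SAP*

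**What the plan says.** The SAP defines total time as the locating time plus the placement time ("defined as the sum of the ultrasound or palpation time, plus the epidural catheter placement time"). The choice of test follows a look at the data: "Distribution normality of continuous data will be examined using box plots and histograms". If times look normal, "Normally distributed continuous variables will be compared using the independent sample Student t-test". Otherwise, "Non-normally distributed data will be compared using the Kruskal-Wallis H test, and continuous data compared with the Mann-Whitney U test". I read the second rule as Mann-Whitney for total time, since there are two groups. The SAP names no covariate, stratified test or model.

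The sample size is left open: "Based on pilot data means and variances, total sample size will be calculated with 80% power to detect a six-minute difference". No SD or N appears in either document.

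On timing, the protocol's section on screening and research activities says "Screening will include an evaluation of the patient's medical history and BMI". The allocation is in an envelope, "which will be revealed to the experimenters only upon opening the envelope at the time of epidural request". The same section has one designated person at each of the two sites do all the marking, after which a different provider places the epidural.

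**The concern.** BMI and site are true baseline variables, because both are fixed before anyone knows the assignment. The protocol also gives a reason to think each may matter. Its Background section links soft tissue over the landmarks to longer procedures. Marking time is part of the endpoint and one person marks at each site, so site carries any difference between the two markers.

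If these variables explain part of the spread in total time, an unadjusted comparison leaves that spread in the error term. The trial then has less power for the six-minute difference than the same patients could give. The choice needs to be fixed in advance, because covariates added after the groups have been compared are open to selection.

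**Working it through.** **Inputs from the SAP:** difference 6 minutes, two-sided alpha 0.05, power 80%. There is no stated N or SD to reproduce.

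**Assumed, not in the documents:** 1:1 allocation; SD of 6, 8 and 10 minutes with total N of 34, 58 and 90, which give the t-test about 80% power; R² of BMI and site together from 0 to 20%.

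**Normal branch.** Power comes from the noncentral t distribution.
- Unadjusted: df = N - 2, noncentrality = 6 / (SD × √(4/N)).
- Adjusted for two covariates: df = N - 4, with the variance multiplied by (1 - R²) × (1 + 2/(N - 5)). The last factor is the price of estimating two covariates.
- Example, N = 34, R² = 0: factor 1 + 2/29 = 1.069, and power falls from 0.807 to 0.779.

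| N (SD) | t-test | R² 0 | R² 5% | R² 10% | R² 20% |
|---|---|---|---|---|---|
| 34 (6) | 0.807 | 0.779 | 0.799 | 0.820 | 0.862 |
| 58 (8) | 0.801 | 0.786 | 0.806 | 0.827 | 0.868 |
| 90 (10) | 0.804 | 0.794 | 0.814 | 0.834 | 0.875 |

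The change is about -1 to -3 points at R² 0, -1 to +1 at 5%, +1 to +3 at 10% and +5 to +7 at 20%. Break-even R² is about 2 to 7%.

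**Small trials.** The same formulas with a smaller assumed SD and R² = 0:
- SD 5, N = 24: 0.802 to 0.758, a loss of about 4 points.
- SD 4, N = 16: 0.797 to 0.717, a loss of 8 points.
- SD 4, N = 14: 0.731 to 0.630, a loss of about 10 points.

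**Non-normal branch.** This was simulated with lognormal errors (sigma 0.6), for a 6-minute shift and for a ratio of 1.5, at N = 34, 58 and 90. Rank analysis of covariance minus Mann-Whitney was about -0.4 to -1.5 points at R² 0, +1.2 to +2.7 at 10% and +3.3 to +7.0 at 20%. Type I error of the rank analysis was 4.9 to 5.2%.

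**Which estimate to report beside the rank test.** With lognormal times, a 6-minute shift and R² = 0, the rank p-value was set beside a robust (HC3) interval for the mean difference. The rank test was significant while that interval included zero in 15.6%, 17.4% and 16.6% of trials at N = 34, 58 and 90, about one in six.

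**How large could R² be?**
- BMI alone: slope needed = √R² × SD / SD of BMI. For R² 10% and an assumed BMI SD of 4 to 6, the lowest value is √0.10 × 6/6 = 0.32 and the highest √0.10 × 10/4 = 0.79 minutes per BMI unit.
- Site alone: R² = share × (1 - share) × d²/SD², with 10 to 50% of patients at the second site. A 2-minute site difference gives 0.4 to 3%, and a 4-minute difference 1 to 11%.

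**The case against.** The strongest reply is that nothing is broken. Randomisation makes the unadjusted tests valid, and a simple test is a respectable choice in a small two-arm trial. That stands, and it is why this is only an optional improvement.

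The benefit also rests wholly on an assumed R², and the documents point towards the low end. BMI is confined to one extreme ("The present study focused on the morbidly obese population"). The Background section reports no attempt yet to enrol at West Penn, and site carries nothing if that continues. The protocol names provider experience as a driver of placement time, but the needle operator is not the marker, so a reader who takes site as a stand-in for operator experience goes further than the design allows. These points limit the gain without removing the option.

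A low cost cannot be taken for granted either. The protocol gives 5 to 10 minutes as a typical placement, so a small pilot SD, and with it a small trial, cannot be excluded. That objection is accepted and sets a lower limit on N below.

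Two practical doubts remain. BMI is assessed at screening, but the contents of the data collection sheet are not given. Enrolment status is stated for West Penn only, so the documents do not show that no outcomes have been seen at Magee. The sponsor can settle both.

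**Conclusion.** The point holds as a cheap improvement that the sponsor could adopt. With a total N of 34 to 90, adjustment costs about 1 to 3 power points on the normal branch if BMI and site explain nothing, and returns about 5 to 7 if they explain 20%. The non-normal branch is similar. All of this depends on assumed SD, N and R², so even the sign of the effect is unknown until pilot data exist.

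Two stronger readings are tempting. One is that the SAP's tests are wrong, or that the design demands a site term. The protocol sends equal numbers of envelopes to each site but does not say that randomisation was stratified, and the unadjusted comparison is valid in any case. The other is that adjustment would surely add substantial power. Nothing in the documents supports an R² of 20% or more.

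**What to change.** Before outcome data are compared by group, add the following to the SAP for the primary outcome, leaving its normality check to pick the branch.

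1. Normal branch: a linear model of total time in minutes on treatment, continuous BMI and site.
2. Non-normal branch: rank analysis of covariance (ranked time on treatment, site and ranked BMI) in place of Mann-Whitney, with that p-value deciding. Report the Hodges-Lehmann shift in minutes with its interval, and state that it is unadjusted. Do not pair the rank p-value with a robust mean-difference interval.
3. Keep the SAP's unadjusted tests as sensitivity analyses.
4. Drop the site term if only one site enrols.
5. If the pilot-based total N is below about 30, keep the unadjusted tests as primary.

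The cost is a few sentences, plus confirmation that BMI and site are recorded for every patient. The statistical price, if the covariates explain nothing, is about 1 to 3 points at N of 34 or more; rule 5 avoids the larger loss in a smaller trial. Because the Hodges-Lehmann interval is unadjusted, it can still sometimes differ from the adjusted p-value, which is why the SAP must say which one decides.

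### The SAP specifies the pooled-variance Student t-test with no provision for unequal variances, and equal arms are not assured; Welch's test is a nearly free safeguard

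*SAP*

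**What the plan says.** The SAP's second paragraph sorts continuous outcomes by their apparent shape: "Distribution normality of continuous data will be examined using box plots and histograms". Those that look normal go to the t-test: "Normally distributed continuous variables will be compared using the independent sample Student t-test". Those that do not go to rank tests: "Non-normally distributed data will be compared using the Kruskal-Wallis H test, and continuous data compared with the Mann-Whitney U test". The SAP mentions no check of equal variance and no unequal-variance version of the t-test. Significance is declared at P ≤ 0.05.

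The primary outcome is total time in minutes. No SD and no sample size are given: "Based on pilot data means and variances, total sample size will be calculated", with 80% power for a six-minute difference at a two-sided alpha of 0.05.

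On allocation, the protocol's description of research activities says: "An online randomizer (Randomization.org) will be used to generate a random order for assignment". Envelopes are shared equally between the two hospitals. That balances sites, not arms. No allocation ratio, blocking or stratification is described.

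**The concern.** Student's t-test estimates one common variance from both arms. Its standard error is right on average if the two variances are equal, or if the two arms are the same size. Otherwise it is too small when the smaller arm is the more variable one, and too large when the larger arm is. P-values are then too small or too large, and a confidence interval built on the pooled variance is too narrow or too wide.

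The documents secure neither condition. Equal arms are not assured. Equal spread is not assured either: the trial hopes for fewer attempts and more first-attempt successes, and total time adds a locating step done by a different method in each arm. Either could change the variance as well as the mean, in a direction that cannot be known in advance. At stake is the accuracy of the primary P-value, if total time is judged normal, and of any other outcome tested this way.

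**Working it through.** The plan states no error rate, SD, sample size or ratio for this test, so there is no figure of its own to reproduce.

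**Inputs**
- From the SAP: two-sided alpha 0.05, power 80%, difference 6 minutes, pooled t-test for normal data.
- Assumed: SD ratio between arms of 1.5 or 2; total N of 40, 58 or 90; simple 1:1 randomisation; normal data.
- Check that the totals are plausible: n per arm = 2 × SD² × (1.960 + 0.842)² / 6². A common SD of 10 minutes gives 200 × 7.85 / 36 = 43.6, so 44 per arm and N = 88. SDs of 5, 8, 12 and 15 minutes give N = 22, 56, 126 and 198.

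**Step 1: when the standard error goes wrong.** The true variance of the mean difference is V = s₁²/n₁ + s₂²/n₂. On average, Student's test uses

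P = [(n₁ − 1)s₁² + (n₂ − 1)s₂²] / (n₁ + n₂ − 2) × (1/n₁ + 1/n₂).

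If n₁ = n₂ = n, both equal (s₁² + s₂²)/n. If s₁ = s₂, both equal s²(1/n₁ + 1/n₂). Only a difference in both size and spread separates them.

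Example, 14:26 with SD ratio 2:
- Smaller arm more variable: V = 4/14 + 1/26 = 0.324. P = (13 × 4 + 25)/38 × (1/14 + 1/26) = 2.026 × 0.1099 = 0.223. √(V/P) = 1.21, so the true standard error is about 21% larger than the one used.
- Larger arm more variable: V = 1/14 + 4/26 = 0.225. P = (13 + 25 × 4)/38 × 0.1099 = 0.327. √(V/P) = 0.83, so the standard error used is too large.

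**Step 2: true error at unfavourable splits.** The splits are the 2.5% points of Binomial(N, 0.5). Student's rejection rate at P ≤ 0.05 with equal means, from 60,000 simulated trials per scenario:

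| Split | SD ratio | Smaller arm more variable | Larger arm more variable |
|---|---|---|---|
| 14:26 | 1.5 | 8.2% | 2.9% |
| 14:26 | 2 | 10.7% | 2.1% |
| 22:36 | 1.5 | 7.3% | 3.2% |
| 22:36 | 2 | 9.2% | 2.5% |
| 36:54 | 1.5 | 7.1% | 3.4% |
| 36:54 | 2 | 8.5% | 2.7% |

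Welch's test stayed at 4.9-5.2% throughout. A repeat with 400,000 trials per scenario agreed with the table to within 0.3 percentage points.

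**Step 3: how likely such splits are.** Under simple randomisation, the chance that the more variable arm is that small or smaller is 4.0% (14 of 40), 4.3% (22 of 58) and 3.6% (36 of 90). A 60:40 or worse split in either direction has probability 27% at N = 40, 10% at N = 64 and 7% at N = 88.

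**Step 4: average over all splits.** Too-high and too-low errors largely cancel. Averaged over simple randomisation, Student's error is about 5.2-5.3% (individual scenarios at SD ratios 1.5 to 2 lie between 5.0% and 5.5%). With exactly equal arms it is about 5%; even at SD ratio 3 it is 4.9-5.5%.

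**Step 5: price of Welch.** With equal variances, simulated power is 80.0% for both tests at 29:29, and 77.9% (Student) against 77.3% (Welch) at 22:36, a loss of 0.6 percentage points.

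**The case against.** The case for leaving the SAP alone is substantial.

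- **The large errors are tail cases.** They need an extreme chance split and an assumed SD ratio together. This stands: over the design as a whole the error is nearly nominal. What survives is that the trial will have one split, and its P-value is read given that split.
- **Randomisation might be taken to be unrestricted.** The documents do not say so. A random order from an online tool could equally be a shuffled list with equal totals, and with equal arms the problem vanishes. This stands. Equal totals on a list would still not assure equal analysed arms. The protocol reports no enrolment yet at the second hospital. If a balanced list of 40 were halved between sites and only one half used (an assumption), a 60:40 or worse split would occur with probability 34%.
- **Ultrasound might be taken to be expected to change the spread.** No passage mentions variability. The stated aim is a shorter total time, with fewer attempts as a secondary aim. A change in spread is possible, but it is an inference.
- **The t-test may not be used at all.** If palpation produces occasional long placements, times would look skewed and go to a rank test. This stands, so the point applies only if times look normal.
- **The sample size might be read as resting on one common SD.** The SAP does not say that; it refers to pilot variances in the plural. No criticism of the sample-size step is made here.

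**Conclusion.** The point holds as a modest, low-severity safeguard. The SAP names a test that relies on equal variances or equal arms, makes no provision for unequal variances, and the protocol does not assure equal arms. At the unfavourable splits examined, the true error would be about 7-11% or 2-4%, depending on which arm is the more variable.

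A reader might infer that the trial's real error rate is half or double 5%. The documents do not support that: those figures depend on assumed SD ratios, assumed totals, normal data and an unlikely split under one possible randomisation method. The expected error of the design stays close to 5%. The case for change rests on low cost and on settling the test before the variances are seen, not on a serious expected bias.

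**What to change.** In the SAP's second paragraph, replace the Student test for normally distributed continuous variables with the Welch unequal-variance t-test. Report the Welch difference in mean minutes with its 95% confidence interval beside the P-value, so that the primary result can be read against the six-minute target.

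The cost is one phrase and one reported interval. The only downside is a negligible loss of power, under one percentage point in the cases checked, when variances are equal. The change does not depend on how the randomisation list was made, so it can be adopted whatever the allocation method proves to be.
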